12.2. Interim Analysis and Stopping Rules

There will be ongoing safety monitoring with periodic safety assessments by the DSMB. There will also be two formal assessments by the DSMB upon certain events within each cohort.

1. For the purposes of the interim toxicity assessment, toxicity is defined as treatment-related SAEs Grade 3 or higher. Toxicity will be formally analyzed in each investigational therapy arm after 12 patients are randomized to investigational therapy. If at least 4 of the first 12 patients randomized to investigational therapy experience toxicity, the study will be stopped; in other words, the threshold for unacceptable toxicity is 30%. If the true toxicity rate is 30%, the probability of stopping is 28%. If the true toxicity rate is 40%, the probability of stopping is 56% and if the true toxicity rate is 20%, then probability of stopping is 7%.
2. If 2 or more subjects in any cohort have their surgery delayed past the scheduled day due to possibly-, probably- or definitely-related adverse effects, as assessed by the treating physician or local Principal Investigator, enrollment to that cohort of the study will be halted, and the trial data will be reviewed by the DSMB to determine whether permanent closure of that arm is appropriate. The occurrence of surgery delay must be documented in the study REDCap database within 24 hours, which will immediately notify the IND-holder and Data Coordinating Center.

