12.6. Sample Size

12.6.1. Sample size considerations

We assumed that reduction in log Ki67 in the endocrine therapy only arm (tamoxifen or fulvestrant, depending on group) will be 50%, based on historical data,⁴⁹ we are using the lower end of this historical range because of data suggesting that tumors that classify as high-risk integrative subtypes are resistant to endocrine therapy.⁵⁰ We assumed that log Ki67 reduction increases to 75% in the integrative subtype-targeted therapy arm based on historical data indicating that an increased reduction by ~25% is associated with clinical benefit (for example, in the IMPACT study, anastrozole induced a reduction of 75% change in proliferation and tamoxifen a reduction of 60% change,⁴⁹ and in neoMONARCH, anastrozole induced a reduction in change of 63% and anastrozole plus abemaciclib a reduction in change of 93% change³⁰).

Assuming a geometric mean ratio of the proportional change of Ki67 of 0.5 (log transformed mean difference of 0.69), standard deviation (log scale) of 1.0, with a one-sided Type I error of 0.10 and a power of at least 0.8, we would need 20 subjects in each treatment arm (40 subjects total per cohort). Based on the drop-out rates seen in neoMONARCH, we have assumed that 80% of subjects in each arm will be eligible for analysis for the primary objective. With these assumptions, we would need to randomize 50 subjects per cohort in order to reach our planned accrual of 40 evaluable subjects (20 subjects per treatment arm, 2 arms per cohort) to reject the null hypothesis under the planned assumptions.

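### The formal toxicity look counts 12 patients by randomisation, with no dosing or follow-up condition, and its action (stopping the study) conflicts with its per-cohort, per-arm scope

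*Combined protocol and SAP*

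**What the plan says.** Section 12.2 announces two formal DSMB assessments, to be made within each cohort.

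For the first, "toxicity is defined as treatment-related SAEs Grade 3 or higher". The trigger is: "Toxicity will be formally analyzed in each investigational therapy arm after 12 patients are randomized to investigational therapy". The boundary and action are: "If at least 4 of the first 12 patients randomized to investigational therapy experience toxicity, the study will be stopped". The section then prints stopping probabilities of 28% at a true rate of 30%, 56% at 40% and 7% at 20%.

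The second assessment concerns surgery delayed by related adverse effects. If it is triggered, "enrollment to that cohort of the study will be halted", and the DSMB then considers whether that arm should close permanently.

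Other parts of the plan that bear on the point:
- Section 4: randomisation comes before treatment starts.
- Section 7.4: SAEs are collected until 30 calendar days after the last administration of investigational product.
- Appendix D, D-1.3.4 and D-5.1.1: zotatifin is a single infusion on Day 1.
- Section 11.2: the DSMB reviews safety data on an ongoing basis.

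**The concern.** A rule of r events in n patients has its stated properties only if all n were exposed and observed for the event. Section 12.2 counts patients once they are randomised. Someone randomised and never dosed cannot have a treatment-related SAE but still takes one of the 12 places. Someone randomised on the day of the look has had no exposure, and the patient before may still be inside the 30-day period. Each such patient enters as a non-event, which makes the formal look less sensitive to toxicity than a look at 12 treated and followed patients.

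The consequence of a crossing is also unclear. The event is counted in one arm of one cohort, but the action names the study. Cohorts 2 and 3 both test zotatifin, so a DSMB facing a crossing in one of them would need to know whether the arm, the cohort or the whole umbrella closes. The text does not tell it.

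**Working it through.** **1. The plan's own figures.** The inputs, from Section 12.2, are n = 12, a boundary of r = 4 or more, and true rates p of 20%, 30% and 40%. The formula is P(stop) = sum over x from r to 12 of C(12, x) p^x (1 − p)^(12 − x).

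| True rate | Printed | At least 4 of 12 (as written) | At least 5 of 12 |
|---|---|---|---|
| 20% | 7% | 0.205 | 0.073 |
| 30% | 28% | 0.507 | 0.276 |
| 40% | 56% | 0.775 | 0.562 |

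At 30%, for example, the probabilities of 0, 1, 2 and 3 events are 0.0138, 0.0712, 0.1678 and 0.2397. They sum to 0.4925, so P(at least 4) = 0.5075. Removing P(exactly 4) = 0.2311 leaves 0.276 for at least 5.

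The written boundary reproduces none of the three printed figures; at least 5 of 12 reproduces all three. In a search over n from 4 to 20 and all boundaries, with a tolerance of two percentage points, n = 12 with r = 5 was the only match.

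**2. Who is unobserved at the 12th randomisation.** Appendix D-8.2 plans about 3 patients per cohort per quarter. At 1:1 that is 1.5 per quarter in the investigational arm, or one about every 90 / 1.5 = 60 days. With one Day 1 infusion and a 30-day SAE period, the 12th patient has no exposure, and on average 30 / 60 = 0.5 of an earlier patient is still inside the window. That earlier patient has been dosed and partly followed. The closest whole-number case is therefore 11 observed out of 12.

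**3. Effect of 11 observed.** The same formula with n = 11 and the unobserved patient counted as a non-event gives:

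| True rate | At least 4: 12 observed | At least 4: 11 observed | At least 5: 12 observed | At least 5: 11 observed |
|---|---|---|---|---|
| 20% | 0.205 | 0.161 | 0.073 | 0.050 |
| 30% | 0.507 | 0.430 | 0.276 | 0.210 |
| 40% | 0.775 | 0.704 | 0.562 | 0.467 |

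Both boundaries are shown because step 1 leaves open which one is meant. Under either, the loss at 30% and 40% is about 7 to 9 percentage points. If the rule is applied only after all 12 have been dosed and followed, there is no loss.

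**4. Scope, set side by side.** In Section 12.2 the assessments are made within each cohort, toxicity is analysed in each investigational arm, rule 1 stops the study, and rule 2 halts the cohort and considers closing the arm. Three of these four statements work at cohort or arm level. Only the action of rule 1 does not.

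**The case against.** The strongest reply is that Section 12.2 does not freeze the data at the 12th randomisation. It asks whether 4 of the first 12 experience toxicity, so later SAEs in those patients can still count. If the DSMB waits for them, the binomial holds. In addition, Section 7.5 requires SAE reports within 24 hours, and the DSMB can recommend stopping at any time, so the formal look is not the only safeguard. All of this is fair and limits the harm. It does not supply the missing condition: nothing in the text tells the DSMB to wait, and waiting does not help with a patient who was never dosed.

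Three stronger readings are tempting, and the documents do not support them.

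- *The printed probabilities differ from those of 4 in 12 because of the trigger or the scope.* They do not. Step 1 shows that the mismatch is one of boundary, and correcting the trigger and scope would leave it in place.
- *Only about 10 of the 12 would be observed, because Section 12.6.1 says* "we have assumed that 80% of subjects in each arm will be eligible for analysis for the primary objective". That figure concerns evaluability for the primary objective, which needs paired Ki67 samples (Section 12.4.1). A dosed patient without a usable second sample can still be fully observed for SAEs. The documents give no rate of undosed patients.
- *A crossing in any one arm closes every cohort, so the chance of closure grows with the number of arms.* This takes the word study literally, against the per-cohort framing of Section 12.2 and against Section 12.4.2, which treats each cohort as an independent trial. In context the cohort is the more natural meaning. The conflict in wording remains, but a multi-arm probability should not be built on it.

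**Conclusion.** The point holds as a defect of definition with a moderate effect. The formal look has no dosing or follow-up condition, and its action does not match its scope. With at least 4 events required, the probability of stopping falls from 0.51 to 0.43 at a 30% rate and from 0.77 to 0.70 at 40%.

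Those figures assume that the look is taken at the 12th randomisation, that accrual runs at the planned pace, that one patient is unobserved and counted as a non-event, and that events are independent with a common rate. Faster accrual or additional undosed patients would increase the loss; waiting for follow-up would remove the part due to incomplete follow-up.

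The larger numerical discrepancy in the same paragraph is separate. At the 30% rate the written boundary stops 50.7% of the time against a printed 28%, and at 20% it stops 20.5% of the time against 7%. The boundary and the probabilities cannot both stand. This review takes no position on which is right.

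**What to change.** - **Count.** Base the look on the first 12 patients in the arm who received investigational therapy and completed the safety follow-up, and do not count undosed patients. State whether accrual continues while the 12 mature.
- **Scope.** Have the sponsor and DSMB reconcile the action of rule 1 with the arm or cohort to which the assessment applies, and use the same term throughout Section 12.2.
- **Probabilities.** Have the sponsor and DSMB reconcile the boundary with the printed figures, and restate the stopping probabilities for the rule and scope that result.

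The cost is an amendment to one section. For the single-infusion arms the formal look comes about one month later. At 1.5 patients per arm per quarter, that is about 1.5 / 3 = 0.5 of a further patient treated before it, while 24-hour SAE reporting and ongoing DSMB review continue.

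### The stated stopping probabilities for the interim toxicity rule (28%, 56%, 7%) belong to a boundary of 5 of 12; the written boundary of 4 of 12 stops with probability 51%, 77% and 21%

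*Combined protocol and SAP*

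**What the plan says.** Section 12.2 (Interim Analysis and Stopping Rules), item 1, defines the event, the timing, the boundary and the boundary's properties.

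- Event: "toxicity is defined as treatment-related SAEs Grade 3 or higher".
- Timing: "Toxicity will be formally analyzed in each investigational therapy arm after 12 patients are randomized to investigational therapy".
- Boundary: "If at least 4 of the first 12 patients randomized to investigational therapy experience toxicity, the study will be stopped". The section glosses this as a 30% threshold for unacceptable toxicity.
- Properties: the stopping probability is given as 28% at a true rate of 30%, 56% at 40% and 7% at 20%.

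Item 2 of the same section is a separate trigger. Two or more related surgery delays in a cohort halt its enrollment pending DSMB review, and no operating characteristics are given for it. Appendix D, Section D-8.1, refers back to the main protocol for further statistical detail, so item 1 governs Cohorts 2 and 3. No other section gives a different toxicity rule or different probabilities.

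**The concern.** The boundary and its probabilities stand in consecutive sentences and should describe the same rule. A stopping chance of only 28% at a true rate of 30% looks low for a boundary of 4 in 12, because the expected count at that rate is 12 × 0.30 = 3.6 events and 4 is close to the middle of the distribution.

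Item 1 is the trial's only toxicity-rate rule with stated operating characteristics, and it is worded as binding. If the properties are wrong, anyone judging the rule from the protocol is misled about how often it stops a tolerable regimen and how often it catches an intolerable one. If instead the properties are what was designed, the written boundary acts one event too early. The two versions part at exactly 4 events in 12: the written rule stops the study, and the rule behind the figures continues.

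**Working it through.** **Inputs (all from Section 12.2).** n = 12 patients randomized to the investigational arm; one formal look; a yes/no toxicity outcome per patient; stop if the count X is 4 or more; true rates p = 0.20, 0.30 and 0.40.

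**Formula.** With X ~ Binomial(12, p), P(X = k) = C(12, k) p^k (1 − p)^(12 − k), and the stopping probability at boundary r is P(X ≥ r) = 1 − [P(X = 0) + … + P(X = r − 1)].

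**Point probabilities.**

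| k | p = 0.20 | p = 0.30 | p = 0.40 |
|---|---|---|---|
| 0 | 0.0687 | 0.0138 | 0.0022 |
| 1 | 0.2062 | 0.0712 | 0.0174 |
| 2 | 0.2835 | 0.1678 | 0.0639 |
| 3 | 0.2362 | 0.2397 | 0.1419 |
| 4 | 0.1329 | 0.2311 | 0.2128 |

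**Step 1: reproduce the plan's figures.** They come out only with r = 5, that is, by subtracting all five rows from 1. (Last digits below come from unrounded terms.)

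**Step 2: apply the written rule.** With r = 4, subtract only the rows k = 0 to 3. At p = 0.30, for example, 1 − (0.0138 + 0.0712 + 0.1678 + 0.2397) = 0.5075.

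| True rate | Stated | Boundary ≥ 5 of 12 | Written boundary ≥ 4 of 12 | Written rule minus stated |
|---|---|---|---|---|
| 20% | 7% | 0.0726 | 0.2054 | 13.5 points |
| 30% | 28% | 0.2763 | 0.5075 | 22.7 points |
| 40% | 56% | 0.5618 | 0.7747 | 21.5 points |

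The ≥ 5 column rounds to the three stated figures exactly. The difference between the two boundaries is the k = 4 row: exactly 4 events has probability 13%, 23% and 21% at the three rates, so the disputed outcome is not remote at the rates the plan itself considers.

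**Step 3: look for another explanation.**

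- Across every rule with n from 3 to 59 and every boundary r, 5 of 12 is the only one that comes within 2 points of all three stated figures.
- The normal approximation to the written rule, with continuity correction (cut at 3.5), gives 21%, 53% and 78% at 20%, 30% and 40%. Without the correction (cut at 4) it gives 12%, 40% and 68%.
- The Poisson approximation to the written rule gives 22%, 48% and 71%.

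No method tried turns the written rule into the stated figures. The pattern is that of a count of more than 4 having been calculated where 4 or more was written.

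**Step 4: size at the 20% rate.** 0.2054 / 0.0726 = 2.8, so the written rule stops nearly three times as often as the boundary behind the stated 7%.

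**The case against.** The arithmetic is not in dispute. The case on the other side concerns the consequences.

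- **The instruction is unambiguous.** The boundary sentence can be carried out as written, and the percentages only describe it. The 30% gloss also fits it: 4/12 = 33% is the first count above 30%, 3/12 = 25% is below, and 5/12 = 42% fits less well. This stands, and it leans towards the boundary being intended and the probabilities being the slip. It does not settle the matter, since all three probabilities consistently describe the other boundary.
- **The error is protective.** The written rule stops sooner than advertised, so no patient faces more toxicity than the text implies. This stands. The cost is a higher chance of closing a tolerable regimen.
- **That cost may be small in practice.** Section D-1.2.1.8 reports possibly related SAEs in 5 subjects (one of the six events was Grade 1), and Table D-1 has N = 72, so the related Grade 3 or higher SAE rate was at most 5/72, about 7%. At that rate P(X ≥ 4) is about 0.7%, and at 10% it is 2.6%. This is a fair guide, although doses, schedules and population differed. It bears on how often the discrepancy would matter, not on whether the stated properties are right.
- **Safety does not rest on this rule alone.** The surgery-delay trigger and the DSMB's ongoing review (Section 11.2) also apply. The DSMB Charter is not among the documents, so what the DSMB was actually shown, and whether the Charter repeats the figures, is unknown.
- **The inferential design is untouched.** Primary endpoint, alpha, power and sample size are unaffected. This is true, but a binding safety rule should still have the properties claimed for it.

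**Conclusion.** The concern holds. All three stated stopping probabilities are wrong for the boundary as written and right for a boundary one event higher. The correct values for 4 or more of 12 are 51%, 77% and 21% at true rates of 30%, 40% and 20%. The discrepancy is about 14 points at 20%, 23 at 30% and 21 at 40%.

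The calculation assumes independent patients with a common toxicity rate, all 12 assessable, and a single look; the stated figures are reproduced under the same assumptions. The documents do not establish which side was intended. It should be corrected, because the plan attributes to a binding safety stopping rule properties that the rule does not have.

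**What to change.** Make the boundary and its properties in Section 12.2, item 1, agree. The sponsor and DSMB should decide which was intended.

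- **If 4 or more of 12 stays:** replace the probabilities with 51% (true rate 30%), 77% (40%) and 21% (20%). The rule and the 30% threshold need no change. The DSMB should confirm that a 21% chance of stopping at a true rate of 20% is acceptable.
- **If 28%, 56% and 7% are the intended properties:** change the boundary to 5 or more of 12, and reconsider the 30% gloss, since 5/12 is 42%.

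Check the DSMB Charter for the same text and align it if needed. The decision should be on record before any cohort reaches its 12-patient look, so that a count of exactly 4 is not argued over after it is known. The cost is a wording amendment of a sentence or two; no patients, data or design changes are needed if the written boundary is kept.

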12.3. Descriptive Statistics and Exploratory Data Analysis

Demographic and other baseline data including disease characteristics will be listed and summarized by study arm. Categorical data will be presented as frequencies and percentages. For continuous data, mean, standard deviation, median, 25th and 75th percentiles will be presented, as appropriate.

12.4. Primary Analysis

12.4.1. Analysis populations

The primary analysis will be conducted on a modified intent-to-treat (mITT) principle. The mITT population will consist of subjects that were randomized and had both baseline and

on-treatment Ki67; subjects will be analyzed by the treatment arm to which they were randomized.

Per-protocol analysis will also be conducted for subjects who do not have any protocol violations and who complete their treatment course. For oral drugs, completing the treatment course is defined as, per self-report, taking at least 80% of the doses of the study drugs including the day prior to surgery or biopsy. Medication compliance for oral drugs will be assessed using a daily drug diary kept by the subject. For injectable/infusion drugs, completing the treatment course is defined as receiving all protocol-mandated injections or infusions.

12.4.2. Analysis plan

For our primary analysis, we will compare the log proportional change of Ki67 between treatment arms using an analysis of covariance (ANCOVA) model adjusting for the log Ki67 at baseline. Geometric LS-means ratio of proportional change (and associated 95% CI) between treatment arms will be calculated from the estimate (and associated 95% CI) of the difference of least squared (LS)-means of the log-proportional change (and associated 95% CI) from the ANCOVA model and converted by antilog transformations. For each treatment arm, geometric LS-means of the proportional change from baseline (and associated 95% CI) will be obtained from the ANCOVA model after conversion by antilog transformations. Geometric LS-means of percentage reduction in Ki67 (and associated 95% confidence intervals) will be calculated with 1 minus geometric LS-means of proportional change (and associated 95% confidence intervals). We will adjust for stratification variables and any differences between treatment arms in baseline covariates, as necessary.

Significance will be determined at a one-sided alpha of 0.1 within each cohort. Because the cohorts are each drawn as separate samples, we consider each to be an independent trial, and no adjustments for multiplicity will be required.

12.5. Secondary Analyses

12.5.1. Analysis populations

For secondary efficacy outcomes, the analysis populations will be the same as the analysis populations for the primary efficacy analysis.

For the exploratory outcome of modified PEPI, the analysis population will be the population of subjects who undergo surgery on study to assess post-treatment Ki67 (excluding those who undergo core biopsy post-treatment instead).

12.5.2. Analysis plan

The proportion of subjects achieving Ki67 < 10% on-treatment will be reported by each treatment arm with Clopper-Pearson 95% confidence intervals. Similarly, the proportion of subjects who undergo surgery who achieve modified PEPI of 0 on treatment will be reported by each treatment arm with Clopper-Pearson 95% confidence intervals. For each of these outcomes, we will conduct a logistic regression model to assess the efficacy of the investigational treatment. We will also compare the log proportional change of Ki67 assessed

through digital pathology between treatment arms using an ANCOVA model adjusting for the log Ki67 at baseline, as in the primary analysis but with digital pathology software-assessed Ki67 rather than pathologist-assessed Ki67.

12.6. Sample Size

12.6.1. Sample size considerations

We assumed that reduction in log Ki67 in the endocrine therapy only arm (tamoxifen or fulvestrant, depending on group) will be 50%, based on historical data,⁴⁹ we are using the lower end of this historical range because of data suggesting that tumors that classify as high-risk integrative subtypes are resistant to endocrine therapy.⁵⁰ We assumed that log Ki67 reduction increases to 75% in the integrative subtype-targeted therapy arm based on historical data indicating that an increased reduction by ~25% is associated with clinical benefit (for example, in the IMPACT study, anastrozole induced a reduction of 75% change in proliferation and tamoxifen a reduction of 60% change,⁴⁹ and in neoMONARCH, anastrozole induced a reduction in change of 63% and anastrozole plus abemaciclib a reduction in change of 93% change³⁰).

Assuming a geometric mean ratio of the proportional change of Ki67 of 0.5 (log transformed mean difference of 0.69), standard deviation (log scale) of 1.0, with a one-sided Type I error of 0.10 and a power of at least 0.8, we would need 20 subjects in each treatment arm (40 subjects total per cohort). Based on the drop-out rates seen in neoMONARCH, we have assumed that 80% of subjects in each arm will be eligible for analysis for the primary objective. With these assumptions, we would need to randomize 50 subjects per cohort in order to reach our planned accrual of 40 evaluable subjects (20 subjects per treatment arm, 2 arms per cohort) to reject the null hypothesis under the planned assumptions.

